5.5 Study Procedures

Before randomization, throughout the study, and following study drug discontinuation, various clinical and diagnostic laboratory evaluations are outlined. The purpose of obtaining these detailed measurements is to ensure adequate **safety and tolerability assessments**. Clinical evaluations and laboratory studies may be repeated more frequently if clinically indicated. The Schedules of Assessments during the screening and treatment period is provided following the Protocol Synopsis. Please see Section C, Schedule of Activities, Table 1, for the schedule for screening phase and treatment phase procedures. Screening assessments will be completed within two days of initiation of duvelisib/placebo.

Screening Phase:

All screening evaluations must be conducted and reviewed by the primary investigator to confirm that patients meet the eligibility criteria. The following procedures will be performed during the screening visit:

- Informed Consent
- Medical History, Physical Exam, Assessment of Performance Status
- Nasopharyngeal swabs for SARS-CoV-2 RT-PCR test, with Ct values for positive tests. Note: saliva SARS-CoV-2 PCR test will be added once available.
- Electrocardiogram (EKG) (if ordered by the primary care team)
- Labs: Complete Blood Count (includes hemoglobin, platelets, and white blood cell count with differential), Comprehensive metabolic panel (includes sodium, potassium, chloride, creatinine, AST, ALT total bilirubin and alkaline phosphatase), Thyroid Stimulating Hormone (TSH), and Covid-19 IgG. Other labs typically (but not always) ordered by the primary care team at the time of screening include: ferritin, D-dimer, CRP, Coagulation Testing (PT/INR, PTT)

Protocol Title: Duvelisib Ameliorates Manifestations of Pneumonia in Established Novel Coronavirus Infection (DAMPEN-CI)

- Non-contrast Chest CT and/or Chest X-ray
- Pregnancy Test (for pre-menopausal women)
- Hepatitis C antibody and Hepatitis B antibodies and viral antigen testing (if known history of treated Hepatitis B or C).

Treatment Phase:

Procedures to be conducted during the treatment phase of the study are presented in the Schedule of Activities (Section C).

- Randomization to duvelisib or placebo arm
- Study drug administration (BID Days 1-14)
- Brief medical history
- Symptom-directed physical exam
- ECOG Performance Status
- Vitals signs, weight, requirement for supplemental oxygen
- Review of prior/concomitant medications
- EKG as ordered by attending physician
- Labs: Complete Blood Count (includes hemoglobin, platelets, and white blood cell count with differential), Comprehensive metabolic panel (includes sodium, potassium, chloride, creatinine, AST, ALT, total bilirubin, and alkaline phosphatase), ferritin, D-dimer, CRP, troponin (abstract from SOC labs daily or as available), Thyroid Stimulating Hormone (TSH, Day 29)
- Immune phenotyping of leukocytes (days 1, 8, 15, and 29)
- Whole blood for RNA – gene expression analyses (days 1, 8, 15, and 29)
- Mononuclear cells for mass cytometry (CyTOF) (days 1, 8, 15, and 29)
- Plasma for cytokine/chemokine analyses (days 1, 8, 15, and 29)
- Serum for antibodies to SARS-CoV-2 (screening and 29)

Follow-up Phase:

- Survival status on day 50 - 60

5.6 Description of Data Collection

Definition of Study Assessments

All patients will be closely monitored for safety and tolerability throughout the study. Patients will continue dosing until they experience intolerable AE's, discharge from hospital, patient withdrawal or termination of the study. Subjects may be discontinued from study treatment in the following situations: 1) subject has decided to withdrawal from the study, 2) Intolerable adverse events, 3) mechanical ventilation (e.g. intubation, high-flow O₂ Bi-PAP or AIRVO) or death, 4) pregnancy, or 5) severe noncompliance. The schedule of activities is listed in section C.

Medical History

Medical history and demographics will be collected at screening. Medical history will include other significant co-morbidities, previous surgeries, history of hypertension, chronic obstructive lung disease, asthma, diabetes, cancer, previous chemotherapy and outcomes, prior immunosuppressive drug therapy including

Protocol Title: Duvelisib Ameliorates Manifestations of Pneumonia in Established Novel Coronavirus Infection (DAMPEN-CI)

steroids, use of tobacco, alcohol and recreational drugs and any known toxin exposure. Demographics data will include age, sex and self-identified race/ethnicity.

Performance Status

The ECOG performance status will be assessed at screening and on days 1 [baseline, prior to study drug], 8, 15, and 29.

Physical Exam

Physical exam will include focused examination of body systems, including assessment of ECOG performance status, weight, heart, lungs, abdomen, skin and nervous system. A targeted physical exam will be performed on screening and on days 1 [baseline, prior to study drug], 8, 15, and 29.

Clinical Assessments

Vital signs will be recorded daily including maximal and minimal blood pressure, heart rate, temperature, oxygen saturation. Daily weights will be recorded. The maximum level of supplemental oxygen delivered in each 24-hour period will be recorded. Results from imaging studies of the lung ordered as part of the standard-of-care management of COVID-19 patients will be extracted from the electronic medical record and entered into case report forms. Positive results from microbiological tests of blood, sputum, and bronchial lavage ordered as part of the standard-of-care management of COVID-19 patients will be extracted from the electronic medical record and entered into case report forms.

Clinical Laboratory Data

Blood samples for chemistry, hematology, viral serologies, leukocyte immunophenotyping and pregnancy (for pre-menopausal patients) will be analyzed at Emory or secondary site clinical laboratories. The chemistry panel will include sodium, potassium, chloride, bicarbonate, glucose, BUN, AST, ALT, total bilirubin, total protein, ferritin, D-dimer, CRP will be tested at screening and on days 1, 8, 15, and 29. TSH will be tested at screening and at day 29. Hematology panel includes complete blood count, including white blood cell count with differential (neutrophils, lymphocytes, eosinophils, basophils), red blood cell count, hemoglobin, hematocrit and platelet count will be tested at screening and days 1, 8, 15, and 29. Hepatitis viral serologies will be tested at screening if a patient has a prior history of treated hepatitis B or C, and include:

- Hepatitis B Panel (HBsAg, HBsAb, HBcAb and HBV DNA PCR)
- Hepatitis C Panel (HCV Ab and HCV PCR)

Correlative Laboratory Data

- SARS-CoV-2 RT-PCR test from nasopharyngeal swabs will be ordered at screening [baseline, prior to study drug]. Results are returned as positive or negative, with Ct values for positive tests. Note: saliva SARS-CoV-2 PCR test will be added once available.
- Leukocyte immunophenotyping (via flow cytometry/fluorescence-activated cell sorting) will be done at days 1, 8, 15, and 29. This will determine the amount of B/T/NK cells and more specifically, the phenotypes and frequencies of these immune cell populations pre and post duvelisib exposure (Th1 and Th17 T cells).
- Mononuclear cells collected at days 1, 8, 15, and 29 will be stored for CyTOF analyses for more in-depth immune-phenotyping in follow-up studies.
- Blood cells collected at days 1, 8, 15, and 29 will also be collected in RNA stabilization tubes for immunological gene expression analyses.

Protocol Title: Duvelisib Ameliorates Manifestations of Pneumonia in Established Novel Coronavirus Infection (DAMPEN-CI)

- Mean levels of inflammatory serum biomarkers will be measured by ELISA at day 1 [baseline, prior to study drug], during and following 2 weeks of study drug exposure in each cohort, using samples at days 1, 8, 15, and 29
- Median titers of neutralizing antibodies to SARS-CoV-2 will be determined at days 1 and 29.

6. Data and Specimen Banking

Specimens will be obtained and used for medical research by the investigators of this study. Data and specimens from this study may be useful for other research being done by investigators at Emory or elsewhere. To help further science, Investigators may provide de-identified data and/or specimens to other researchers. Any information that could identify participants will not be included. If data or specimens are labeled with study ID, we will not allow other investigators to link that ID to identifiable information.

Samples and data collected under this protocol may be used to study **COVID-19**. Access to stored samples will be limited to IRB-approved investigators. Samples and data will be stored using codes assigned by the investigators or their designees. Data will be kept in password-protected computers. Only investigators will have access to the samples and data.

All stored samples will be maintained in the laboratory to which it was sent initially for analysis. Study participants who request destruction of samples will be notified of compliance with such request and all supporting details will be maintained for tracking.

The results of some study tests and procedures will be used only for research purposes and will not be placed in subject's medical record.

7. Sharing of Results with Participants

In general, study staff will not provide any individual results to subjects (ex. outcome trial results or results from subject's samples studies). If something of urgent medical importance to the participating subjects will be found, the PI (or co-Is) will inform the subject, although we expect that this will be a very rare occurrence. Samples and data will only be used for research.

8. Study Timelines

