1.2 Schedule of Assessments

Following screening, informed consent, and confirmation that a patient with severe COVID-19 meets all eligibility criteria, subjects will be randomized 1:1 to receive duvelisib 25 mg, po BID or a placebo pill, po BID. Randomization between duvelisib 25 mg po BID and placebo BID will be stratified by study site. The investigational pharmacy will supply coded study drug based upon the results of central randomization.

Procedures and Tests Study Tests DURING HOSPITALIZATION [#]	Days -2 to 0 [@]	Day 1 [@]	Day 8 (± 2)	Day 15 (± 2)	Day 29 (± 3)	Day 50-60
Randomization to duvelisib or placebo arm	X					
Study Drug Administration		Oral drug BID Days 1-14				
SARS-CoV-2 RT-PCR	X					
Immunophenotyping of immune cells in blood		X	X	X	X	
Whole blood for RNA gene expression ^{##}		X	X	X	X	
Mononuclear cells for mass cytometry ^{##}		X	X	X	X	
Plasma cytokines and chemokines ^{##}		X	X	X	X	
Anti-SARS Cov-2 IgG		X			X	
TSH	X				X	
Hepatitis Serologies if known history of treated Hepatitis B or C	X					

Standard of Care Tests*	Days -2 to 0	Day 1	Day 8 (± 2)	Day 15 (± 2)	Day 29 (± 3)	Day 50-60
Physical Exam	X	Performed daily during hospitalization				
ECOG Performance Status	X	Performed daily during hospitalization				
Vital Signs	X	Performed daily during hospitalization				
Clinical Labs: Record data in eCRF (REDCap) during hospitalization as shown below						
CBC with differential	X	Abstract data as available				
CMP	X	Abstract data as available				
Ferritin		Abstract data as available				
CRP, Troponin		Abstract data as available				
Coagulation Tests**		Abstract data as available				
Non-contrast Chest CT or Chest X-Ray	X	Abstract data as available				
Serum or Urine Pregnancy Test***	X					
Assessment of Survival Status						X

study procedures which are performed as part of the research protocol and covered by the study budget

Additional research blood samples will be obtained prior to discharge from hospital

@ Some overlap of procedures and tests performed for screening and Day 1 is expected.

* Standard of care procedures which are routinely performed on COVID-19 patients and the results of which will be recorded as part of study conduct

** PT/INR, PTT, Fibrinogen, D-Dimer, Heparin/Enoxaparin Anti Xa

*** Pregnancy test for WOCBP may be obtained after hospital admission but prior to study enrollment

2. Objectives (and Endpoints)

OBJECTIVES	ENDPOINTS
Primary	

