To compare the incidence of mechanical ventilation or death in subjects with severe COVID-19 given placebo or oral duvelisib.	The primary end-point is a composite endpoint of mechanical ventilation or death within 4 weeks of randomization.
Secondary	
Secondary Objectives are to compare the duvelisib cohort to the placebo cohort with respect to:
 
1) Days to recovery as assessed by ACTT endpoints as the time to recovery (Day 1 through Day 29) to satisfy a score of ≥ 5 from the following eight categories from the NIAID ordinal scale. The scale is as follows: 1. Death; 2. Hospitalized, on invasive mechanical ventilation or extracorporeal membrane oxygenation (ECMO); 3. Hospitalized, on non-invasive ventilation or high flow oxygen devices; 4. Hospitalized, requiring supplemental oxygen; 5. Hospitalized, not requiring supplemental oxygen - requiring ongoing medical care (COVID-19 related or otherwise); 6. Hospitalized, not requiring supplemental oxygen - no longer requires ongoing medical care; 7. Not hospitalized, limitation on activities and/or requiring home oxygen; 8. Not hospitalized, no limitations on activities.2) Duration of hospitalization3) Death within 29 days of randomization4) ICU transfer within 29 days of randomization5) ECOG performance status at day 15 and 29 of randomization6) Incidence of grade III-V adverse events or SAEs (as defined by CTCAE version 5)7) Documented secondary bacterial or viral infection within 29 days of randomization.8) Mean frequencies of Th1 and Th17 T cells in blood mononuclear cells at 1, 2 and 4 weeks9) Mean levels of inflammatory serum biomarkers at 1, 2 and 4 weeks10) Gene expression profiles of T cells at 1, 2 and 4 weeks

OBJECTIVES	ENDPOINTS
11) Median titers of IgG antibodies to SARS-CoV-2 at 4 weeks 12) Survival at day 50-60 after randomization	

3. Background

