8.1 Duration of therapy and follow up

In the absence of treatment delays due to adverse event(s), subjects will be treated for 14 days with duvelisib/placebo. A subject will be considered to have completed the study if he or she has completed all phases of the study including the last visit or the last scheduled procedure shown in the schedule of activities. Subjects who have signed consent, are deemed eligible and are randomized to receive study drug (duvelisib/placebo) will be considered evaluable for efficacy endpoints on an intent-to-treat basis. Subjects who receive at least one dose of study drug (duvelisib/placebo) will be evaluable for toxicity. The end of the study is defined as completion of the last visit or procedure in SOA (Day 29) and an assessment of survival status on day 50 - 60. In the event of a subject's withdrawal, the Investigator will make every effort to complete the End of Treatment procedures specified in the Schedule of Events. Subjects who withdraw from the study will be encouraged to permit follow-up for clinical end-points, including death, mechanical ventilation (e.g. intubation, high-flow O₂ Bi-PAP or AIRVO), hospital discharge, and need for supplemental oxygenation. Subjects will be assessed daily while hospitalized. If the subjects are discharged from the hospital, they will have phone follow-up calls with a study team member at

Protocol Title: Duvelisib Ameliorates Manifestations of Pneumonia in Established Novel Coronavirus Infection (DAMPEN-CI)

day 15 (window d13 – 25), and at day 29 (window d27 - 39) for clinical outcomes data. Arrangements will be made for an outpatient phlebotomy appointment after day 29 (day 30 - day 60 if possible, but up to day 100) to obtain safety laboratory tests and blood samples for secondary research. Patients will receive \$100 compensation for the in-person follow-up phlebotomy visit. However, travel distance, infection control or other restrictions may limit the ability of the subject to return to the clinic. In such cases, only clinical data will be obtained via the d27 - 39 call.

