Evaluable subjects will be all subjects who were randomized to receive duvelisib or placebo. The definition of secondary endpoints are listed in section 2. The descriptive statistics will mainly be applied to all secondary endpoints by treatment arms separately, such as frequency and percentage for categorical endpoints and mean, median, and standard deviation for numerical endpoints. They will be compared between treatment arms by Fisher's Exact test for categorical endpoints and Wilcoxon Rank-Sum test for numerical endpoints. For biomarkers measured repeated over time, generalized estimating equation (GEE) model will be used to test the difference in change pattern over time by two treatment groups using a nonlinear model. P-value will be adjusted for multiple comparison if necessary. Time to recovery is as the days from randomization to reach the desired NIAID ordinal scale ≥ 5 , a log-rank test will be used to compare the difference between the two arms. Survival rate at day 50 - 60 will be estimated by Kaplan-Meier method with log-rank test.

Interim Analysis for futility

The responsibility of any data-informed recommendations regarding continuing/stopping the study or modifying the study design/protocol be restricted to the independent data monitoring committee (IDMC), which is a part of the Winship data safety monitoring committee (DSMC). Upon 20 enrolled for each arm, an interim analysis will be carried out by two-sided Mantel-Haenszel test. O'Brien-Fleming boundary for futility is 2.373 on the Z score (equivalently: 0.991 on the fixed sample p-value scale). The trial may be terminated due to futility, or

Protocol Title: Duvelisib Ameliorates Manifestations of Pneumonia in Established Novel Coronavirus Infection (DAMPEN-CI)

following review by the IDMC of clinical and laboratory immune-monitoring data. Otherwise, the trial will continue enrolling patients until all 80 patients enrolled.

Stopping Rule for Safety

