All patients who maintain consent to be followed for additional outcome information will remain in the study through the end of the double-blind period collection of safety and efficacy assessments. Subjects discharged from the hospital prior to the last protocol-specified assessment on day 29 will be followed as out-patients with in-person or telehealth visits. Survival status at day 50 - 60 will be captured in all subjects who have not withdrawn consent for follow-up by contacting the patient via a telehealth visit or other approaches (e.g., telephone calls, texts, and emails to the patient and close contacts). In the absence of direct or indirect contact with the subject, a vital records search will be performed to assess survival status of each subject.

Data Retention

All study documents will be retained for at least two years after the last approval of a marketing application in their country and until there are no pending or contemplated marketing applications in their country.

Transmission of Data:

Blood samples for T-cell phenotyping from secondary sites will be cryopreserved and shipped to Emory University in real-time. Patient samples will be cryopreserved by using Crystor Media (please see Appendix F). Emory University will cover the cost of shipment of blood samples. All patient samples for T-cell phenotyping will be analyzed at Emory University to ensure uniform analysis. Clinical data (ORR and rates of CRS, neurotoxicity, ICU

transfers) will be captured with chart review at Emory University and secondary sites. Data will be uploaded into RedCap. There will be monthly meetings (tele-conference) with each site's PI to review the study, enrollment and reporting of data.

Publication Plan

The results of the study should be available within 12 months of completion of the study. The end of the study is the time point at which the last data items are to be reported or after the outcome data are sufficiently mature for analysis. A full report of the outcomes will be made public no later than three years after the end of the study.

16. Provisions to Monitor the Data to Ensure the Safety of Participants

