- Due to the wide array of symptoms experienced by patients hospitalized with COVID-19, it is not feasible or informative to record and assess all possible symptoms and lab test results for AE/SAE grading in this study. Hence AE/SAE grading and reporting will be limited to lab tests that might reflect effects of study drug exposure including bilirubin, ALT, ALK PHOS, AST, leukopenia, lymphopenia, anemia, and thrombocytopenia. Symptomatic AE/SAE grading and reporting will focus on the following: diarrhea, bradycardia, symptoms requiring ICU admission and mechanical ventilation, symptoms requiring repeat hospitalization, or death. Non-clinically relevant AEs (Grade 1) will not be included on AE logs or AE reporting documents.

Classification of an Adverse Event

Severity of Event

For both AE's and SAE's the investigator must assess the severity of the event. The severity of the event will be graded based off the patient's symptoms using the Common Terminology Criteria for Adverse Events (CTCAE Version 5.0):

https://ctep.cancer.gov/protocoldevelopment/electronic_applications/docs/CTCAE_v5_Quick_Reference_5x7.pdf.

The terms "severe" and "serious" are not synonymous. Severity refers to the intensity of an AE (as in mild, moderate, or severe pain); the event itself may be of relatively minor medical significance (such as severe headache). "Serious" is a regulatory definition and is based on patient or event outcome or action criteria usually associated with events that pose a threat to a patient's life or vital functions. Seriousness (not severity) serves as the guide for defining regulatory reporting obligations

Relationship to Study Intervention

All adverse events (AEs) must have their relationship to study intervention assessed by the clinician who examines and evaluates the participant based on temporal relationship and his/her clinical judgment. The degree of certainty about causality will be graded using the categories below. In a clinical trial, the study product must always be suspect.

Expectedness

Principal Investigator will be responsible for determining whether an adverse event (AE) is expected or unexpected.

An **expected** adverse event is those that have previously identified resulting from administration of the study drug. These include, but not limited to, AE's that are listed in the AE list, stated on the informed consent document or listed on the investigator's brochure.

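### No post-discharge ascertainment is specified for secondary infection within 29 days, so an arm discharged sooner would tend to record fewer infections at equal true risk

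*Combined protocol and SAP*

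**What the plan says.** - **Endpoint.** Section 2 and the synopsis list "Documented secondary bacterial or viral infection within 29 days of randomization" among the secondary endpoints. No case definition is given and no cultures are scheduled.
- **Source.** Section 5.6, under Clinical Assessments, says: "Positive results from microbiological tests of blood, sputum, and bronchial lavage ordered as part of the standard-of-care management of COVID-19 patients will be extracted". The results are taken out of the hospital chart and transferred to the study's case report forms. No other passage names a source for this endpoint.
- **Contact in hospital.** Section 8.1: "Subjects will be assessed daily while hospitalized".
- **Contact after discharge.** Section 8.1 says of discharged patients that "they will have phone follow-up calls with a study team member at" about Day 15 and Day 29, to collect clinical outcomes that it does not itemise. Where Section 8.1 does list endpoints for continued follow-up (after withdrawal or removal for toxicity), it names death, ventilation, discharge and oxygen need, but not infection. Section 15.2 adds: "Subjects discharged from the hospital prior to the last protocol-specified assessment on day 29 will be followed as out-patients with in-person or telehealth visits". That sentence stands under the heading on capturing the primary endpoint.
- **Adverse events.** Section 16.2 limits grading and reporting to selected laboratory tests plus diarrhoea, bradycardia and "symptoms requiring ICU admission and mechanical ventilation, symptoms requiring repeat hospitalization, or death". Infection is not listed.
- **Analysis.** Section 15.1, on secondary endpoints: "Evaluable subjects will be all subjects who were randomized to receive duvelisib or placebo". Categorical endpoints are compared by Fisher's exact test. Missing secondary data are not imputed and analyses use observed cases.

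**The concern.** The window is the same 29 days for everyone, but the intensity of observation is not. An inpatient is seen daily and cultured when clinically indicated. A discharged patient has two contacts at which no one is instructed to ask about infection. Days after discharge stay inside the window with little specified means of finding an event.

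This would matter little if both arms spent equal time in hospital. The trial's hypothesis makes a difference plausible: it is sized for death or ventilation falling from 40% to 15%, and duration of hospitalisation is itself a secondary endpoint. Blinding does not remove a difference in observation time that the treatment itself produces. Sputum and lavage sampling may also track ventilation.

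The direction is unhelpful. Section 13 names infection as a duvelisib risk, reported in 61-69% of patients in earlier trials. If the drug shortens stays, the infection comparison leans towards reassurance in just the case where the drug would be taken forward.

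**Working it through.** **Plan's own figure.** There is none to reproduce: the documents give no infection rate, length of stay or power for this endpoint. What follows shows direction and plausible size only.

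**Inputs.**
- From Section 15.1: 40% (placebo) and 15% (duvelisib) with the composite of death or mechanical ventilation, and 40 patients per arm.
- Assumed: a 22-day stay with the composite event and 8 days without; infection hazard h = 0.015 per day; every in-hospital infection detected.

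**1. Days observed.** Mean = p × 22 + (1 − p) × 8.
- Placebo: 0.40 × 22 + 0.60 × 8 = 13.6 days
- Duvelisib: 0.15 × 22 + 0.85 × 8 = 10.1 days, a ratio of 0.743

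**2. Recorded proportion, equal hazard, no post-discharge capture.** p(1 − e^(−22h)) + (1 − p)(1 − e^(−8h)), where 1 − e^(−0.33) = 0.281 and 1 − e^(−0.12) = 0.113.
- Placebo: 0.40 × 0.281 + 0.60 × 0.113 = 18.0% (7.2 of 40)
- Duvelisib: 0.15 × 0.281 + 0.85 × 0.113 = 13.8% (5.5 of 40)
- Ratio 0.77. With stays of 20/7, 22/8 or 25/10 days and h of 0.005 to 0.03, the ratio runs from 0.74 (20/7, 0.005: 4.35% / 5.87%) to 0.82 (25/10, 0.03: 29.9% / 36.7%).

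**3. True excess on duvelisib.** Multiply h by the hazard ratio in that arm.
- 1.35: 18.1% against 18.0%, so the excess is hidden.
- 2.0: 25.4% against 18.0%, so the excess is visible.

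**4. How much of the 4.2-point gap is bias?** Let the hazard at home be k times the inpatient hazard and count every infection to Day 29: p(1 − e^(−h(22 + 7k))) + (1 − p)(1 − e^(−h(8 + 21k))).

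| k | Placebo | Duvelisib | Real gap | Bias within 4.2 points |
|---|---|---|---|---|
| 1 | 35.3% | 35.3% | 0 | 4.2 |
| 0.5 | 27.3% | 25.4% | 1.9 | 2.3 |
| 0.2 | 21.9% | 18.7% | 3.2 | 1.0 |
| 0 | 18.0% | 13.8% | 4.2 | 0 |

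**5. Partial capture (k = 1).** If a fraction s of post-discharge infections is found anyway, recorded = in-hospital + s × (35.3% − in-hospital).
- s = 0.25: 22.3% against 19.2%, ratio 0.86
- s = 0.5: 26.7% against 24.6%, ratio 0.92

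**6. A second model as a check.** Constant hazard λ = −ln(1 − R)/29, exponential stay with median m, S(t) = 0.5^(t/m); recorded risk = ∫ λe^(−λt)[S(t) + s(1 − S(t))]dt over 0 to 29 days. Assumed: true risk R = 20% in both arms and median stay 14 against 7 days.
- s = 0: 10.9% against 6.9% (ratio 0.63)
- s = 0.25: 13.2% against 10.2% (0.77)
- s = 0.5: 15.4% against 13.4% (0.87)
- s = 1: 20% in both arms
- Medians of 14 against 10 days, s = 0: ratio 0.82
- All infections spread evenly over the first 7 days, s = 0: 16.9% against 14.4%
- True risks 20% and 30%: at s = 0 recorded as 10.9% and 10.6% (masked); at s = 0.25 as 13.2% and 15.5% (visible)
- True risks 20% and 40%, s = 0: 10.9% and 14.6% (visible)

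**7. Effect on the test.** With 40 per arm and the s = 0 case at R = 20%, Fisher's p ≤ 0.05 occurs with probability 3.4%, against 2.8% with full capture. The bias would show in the descriptive rates, hardly ever as a false significant result.

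**The case against.** **Post-discharge routes exist.** Section 15.2 provides outpatient or telehealth follow-up to Day 29, Section 16.1 has the investigator ask about adverse events at each study visit, and readmission is reportable. Section 5.6 does not confine extraction to the index admission. A reader might infer that infections are sought only in hospital, and cite the schedule's instruction, "Record data in eCRF (REDCap) during hospitalization as shown below". That row heads the clinical laboratory tests and does not list microbiology, so it does not support the inference. What stands is that capture after discharge is unspecified and incomplete, not absent.

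**A large harm would not disappear.** A reader might infer that the arm with shorter stays shows fewer infections whatever the true risk. Steps 3 and 6 refute this: a doubled hazard, or a true 40% against 20%, is still recorded as an excess.

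**Part of the gap may be real.** If leaving hospital or avoiding ventilation lowers infection risk, fewer infections are a genuine effect. Step 4 shows this can account for most of the illustrated gap. This objection stands.

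**The inputs may overstate the difference.** The 40% and 15% count deaths, and Section 15.1 counts high-flow oxygen and Bi-PAP as ventilation. Early deaths and high-flow patients with shorter stays would probably narrow the difference in observed days. This also stands.

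**The consequence is limited.** This is one of about a dozen secondary endpoints, analysed mainly descriptively in a blinded trial with identical procedures in both arms. Exposure is at most 14 days, whereas Section 3.1 ties opportunistic infection to months of exposure. If stays and culturing do not differ by arm, the bias largely vanishes.

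**The denominator is not fully settled.** The observed-case rule does not say whether a discharged patient without a culture is negative or missing. This is a further gap to close and does not answer the point.

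**Conclusion.** The point holds in conditional form. The plan specifies no post-discharge ascertainment of infection and makes no allowance for observation time. If stays differ by arm, the arm discharged sooner would tend to record fewer infections at equal true risk, and a moderate excess could be masked.

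The size cannot be fixed from the documents. The illustration of 18.0% against 13.8% assumes 22- and 8-day stays, a 1.5% daily risk, no post-discharge capture, and composite-event rates of 40% and 15% as the share with long stays. The gap is all bias if home risk equals inpatient risk, about half (2.3 of 4.2 points) if home risk is half, and nil if it is zero. Any post-discharge capture shrinks the bias further.

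The primary analysis is untouched. The change is still worth making because it is cheap, infection is a named risk of the drug, and information not sought by Day 29 is hard to recover later.

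**What to change.** 1. At the existing Day 15 and Day 29 contacts, ask every discharged patient about infection diagnosed or treated since discharge, and abstract available outpatient and readmission records through Day 29.
2. State how a discharged patient with no culture is counted: negative or missing.
3. Show culture-proven and reported infections separately and combined, by arm.
4. Add a supportive rate of infection per inpatient day by arm.

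The cost is a few questions at contacts already scheduled, some record abstraction and one supportive table. The downside is that post-discharge reports are less often culture-proven, which is why item 3 keeps the two kinds apart.
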